## 7 Site and Investigator selection

We intend to recruit 100 Primary Care practices across the UK. These will be managed through three study hubs. The networks with whom we have outline agreement to facilitate the study are; Wales Primary Care ('PiCRIS') Research Network; North East England and North Cumbria Research Network and Western Research Network. We may approach other Research Networks across the UK if required.

All GP sites who are interested in participating in the study will be required to complete a registration form to confirm that they have adequate resources and experience to conduct the study. This will be facilitated by each local research network hub.

Before any Site can begin recruitment a Principal Investigator at each site must be identified. The following documents must be in place and copies sent to the PriMUS Study email account (see contact details on page 4):

- The approval letter from the site's R&D Department, following submission of the Site Specific Information (SSI) form
- A signed Study Agreement
- Current Curriculum Vitae and GCP training certificate of the Principal Investigator (PI)
- Completed Site Delegation Log and Roles and Responsibilities document
- Full contact details for all host organisation personnel involved, indicating preferred contact
- A copy of the most recent approved version of the Participant Information Sheet(s) and Consent Form(s) on host care organisation headed paper
- A copy of the most recent approved GP letter on host care organisation headed paper

Upon receipt of all the above documents, the Study Manager will send written confirmation to the Principal Investigator/lead Researcher detailing that the site is now ready to recruit participants into the study. This letter/email must be filed in each site's Site File. Along with the written confirmation, the site should receive a study pack holding all the documents required to recruit into the study.

Occasionally during the study, amendments may be made to the study documentation listed above. The Cardiff University Centre for Trials Research (CTR) will issue the site with the latest version of the documents as soon as they become available. It is the responsibility of the CTR to ensure that they obtain local R&D approval for the new documents.

Site initiation will be by launch meeting or by teleconference if attendance of key personnel is unfeasible.

## 8 Participant Selection

Adult ( $\geq 16$  years) men who consult with their GP with one or more bothersome Lower Urinary Tract Symptoms (LUTS).

Participants are eligible for the study if they meet all of the following inclusion criteria and none of the exclusion criteria apply. All queries about participant eligibility should be directed to the Study Manager or local Network Researcher before registration.

### 8.1 Inclusion /Exclusion criteria

Inclusion Criteria	Exclusion criteria

 
• Men aged 16 years and over.
 
• Men who present to their GP with a complaint of one or more bothersome lower urinary tract symptoms#
 
• Men able and willing to give informed consent for participation in study
 
• Men able and willing to undergo all index tests and reference test, and complete study documentation.
 
 
# This would include men on current treatment, but who are still symptomatic
	
 
• Men with neurological disease or injury affecting lower urinary tract function
 
• Men with LUTS considered secondary to current or past invasive treatment or radiotherapy for pelvic disease Men with other contraindications to urodynamics e.g. Heart valve or joint replacement surgery within the last 3 months, immunocompromised/immunosuppressed.
 
• Men with indwelling urinary catheters or who carry out intermittent self-catheterisation
 
• Men whose initial assessment suggests that clinical findings are suggestive of possible:               
 
○ prostate or bladder cancer*
 
○ recurrent or persistent symptomatic UTI**
 
○ renal impairment
 
○ retention
 
 
 
• Men unable to consent in English or Welsh where a suitable translator is not available. This is a multi-centre study based in primary care, and we cannot guarantee translation facilities at all sites
 
 
*According to standard NHS cancer pathways. If later deemed unlikely, then eligible for study participation.
 
**If UTI successfully treated but LUTS remain, then eligible for study.

	
>This is a multi-centre study based in primary care, and we cannot guarantee translation facilities at all sites.

## **9 Recruitment, Screening and Registration**

### **9.1 Participant identification**

Potential participants will be recruited from primary care practices across the three network hubs. Recruitment strategies may differ between hubs depending on local geographic and organisational factors.

Participating practices will conduct a search of their patient electronic records using 'pre-defined read codes' to identify all potentially eligible patients who have presented within the last 6 month(s) at the start of the study and at least three additional times throughout the duration of the study. These patients will be 'flagged' in their general practice clinical record using pre-specified read codes in order to allow easy identification of patients, when they contact the surgery, who could be eligible to participate.

Practices will have the option to send relevant patients a letter informing them about the study (on practice headed paper) and a Patient Information Summary Leaflet, and invite the patient to attend the practice for a consultation.

Study posters, leaflets and adverts using electronic visual aids (where appropriate) will be used in practice waiting areas to inform patients about the study.

Participating clinicians will also be asked to approach eligible patients opportunistically during routine practice sessions.

Upon presentation, the PriMUS study will be introduced and the patient information pack (including the Patient Information Sheet, Patient Information Summary Leaflet, Consent Form, Urodynamics Leaflet and Frequency Volume Chart) provided to the patient during their primary care consultation for a complaint of lower urinary tract symptoms.

The GP will have the option to consent a patient to enter the study during the initial consultation visit, if the patient meets the eligibility criteria and they feel this is appropriate. If the patient is not consented during the initial GP Consultation, those who express interest will complete the Consent to Contact Form, which will be passed to the local research nurse. The patient will be contacted by telephone ideally within a week by a research nurse based at the local research network hub, and invited to attend a study appointment.

The GP will complete the Digital Rectal Examination (DRE), Prostate Specific Antigen (PSA) Test and the Physical Examination, (as outlined in NICE clinical guideline CG97) and complete the eligibility checklist, confirming the patient is eligible to enter the study. The GP will also be required to record the results from these tests on a separate eligibility results form. At the study visit with the research nurse, the study will be explained in more detail and the research nurse will establish whether or not the patient wishes to take part. Those who are happy to enter and are eligible will be asked to provide informed consent.

During this appointment, the patient will complete the ICIQ Male LUTS symptom questionnaire and the IPSS questionnaire. The research nurse will complete the patient registration CRF, which will include data collection for the remaining study index tests (i.e. medical history and demographics).

If possible, the research nurse will arrange for the participant to undergo the reference test of (urodynamics) at the same study visit to minimise patient burden, however, in some circumstances this may take place as two separate study visits. This will preferably be performed by the research nurse at the GP practice but with access to the local urology service if required. In some circumstances the urodynamics may take place in a secondary care setting.

## **9.2 Screening logs**

A screening log of all ineligible and eligible but not consented/not approached will be kept at each site to inform adjustment of recruitment strategies and study processes. The logs will also be used to assess any selection bias prejudicing generalisability of the decision aid. When at site, logs may contain identifiable information but this **must** be redacted prior to being sent to the CTR. The screening log should be sent to the study specific email address ([contact]) every month (see section 24 for further detail on data monitoring/quality assurance).

## **9.3 Informed consent**

Eligible patients will be given as much time as they need after the initial invitation to participate before being asked to sign the consent form. GPs will have the option to consent a patient during the initial consultation visit, if the patient meets the criteria and the GP feels this is appropriate. Patients will be notified that they can withdraw consent for their participation in the study at any time during the study period. Patients will also be informed that they have the right to refuse entry to the study without giving a reason and that this will not affect their care in any way.

Informed consent from patients will be sought by suitably qualified, experienced and trained personnel in accordance with the GCP directive on taking consent and before any study related procedures are undertaken.

Patients will be asked to sign a consent form. One copy will be given to the patient, one copy kept in the Site File and a copy sent to the CTR. A further scanned copy will be kept in the patient's record.

Only when written informed consent has been obtained from the patient and they have been enrolled into the study can they be considered a study participant. Once consented, participants will be allocated a unique study number (participant ID), which will be the primary identifier for all participants in the study.

The participant will remain free to withdraw at any time from the protocol without giving reasons and without prejudicing their further treatment.

Separate informed consent will also be taken for participation in the qualitative interviews. The main study consent form will include consent to be contacted for the qualitative interview (patients will be reminded that participation in the main study does not mean that they must participate in the qualitative interview). The qualitative researcher will select a sample of patients and the patient will be sent an interview study patient information sheet and a consent form. When the consent form has been received, the researcher will contact the patient to arrange a convenient time / location for interview. We also aim to interview patients who do not agree to take part in the main study. If a patient declines to participate in the main study, the personnel responsible for recruitment will invite them to take part in the interview study. If they agree, they will be given an interview study information sheet, study reply form, and consent form. These can be returned to the research team using a pre-paid self-addressed envelope.

We will comply with Welsh language requirements and the PIS, Consent Form and any other required participant documentation will be available in Welsh. However, all documentation used for data collection (i.e. outcome measures) will remain in English as they are designed and validated in English.

#### **9.4 Registration**

Eligible participants who have consented to take part in the study will be registered by recording key information including; contact details, past medical and medication history, as well as demographics.

## **10 Study Intervention**

### **10.1 Decision aid**

Results from the index tests collected from the first cohort will be used to develop a statistical model which will form the engine behind our clinical decision aid. This decision aid will combine results from the simple tests performed in primary care, to best predict urodynamic diagnosis (detrusor overactivity during bladder filling, bladder outlet obstruction and detrusor underactivity during voiding).

The presence or absence of nocturnal polyuria will not be included in this decision aid but will be separately assessed and included as an addendum to the diagnostic prediction. The resulting decision aid will provide probabilities for each of the three possible diagnoses. Qualitative work with expert consensus groups, conducted in parallel with the study will develop management decisions recommendations and thresholds for clinically useful diagnostic prediction in order to map the diagnoses predicted by the statistical model to current guidelines.

Acceptability of the decision aid to patients and clinicians will be assessed in the latter part of the study by use of a prototype decision aid. This prototype will be created using Shiny, a web application framework for the statistical programming language R. The prototype will be presented as an online tool, where the primary care staff input index test variables into an online form akin to the QRISK2® calculator (12). Once the form is submitted, a screen showing the index test results, and diagnostic probabilities and management recommendations will be displayed.

We will investigate the feasibility of automatic extraction of these test results, along with patient characteristics (demographics and other clinical), from the electronic record as well as the automated upload of these results into GPs' patient administration systems or simply saving as a document into the patient's record upon study completion.

### **10.2 Index tests**

Our literature review (Oct 2015), updating the results of the NICE Guideline review, identified the investigations listed in Table 1 below as having potential value in diagnosing the cause of LUTS and which we will consider as index tests in the study.

**Table 1**

Test	Details	Result	Visit
Relevant demographics	Following assessment for eligibility and agreement to participate	Age in years	Identification/screening
Physical examination of abdomen	Carried out by competent primary care health professional. To palpate for a distended bladder.	Bladder palpable/not palpable	First GP consultation
Digital rectal examination	Carried out by competent primary care health professional. To determine prostate enlargement and likelihood of locally advanced prostate cancer.	Prostate mild/moderate/severe enlargement Further assessment for prostate cancer required/not required	First GP consultation
Prostate specific antigen	Single blood test. To compare value against NHS-defined thresholds	PSA value – established thresholds for further assessment for prostate cancer (typically > 3 ng/mL) or benign enlargement (typically ≥ 1.5 ng/mL) For decision aid: continuous variable in ng/mL	First GP consultation
ICIQ-Male LUTS* symptom questionnaire	Patient-completed validated questionnaire which defines presence, type and severity of LUTS	Total score (0-44); Voiding symptom score (0-20), storage symptom score (0-24), quality of life score (0-4).	Study Visit, Part A
IPSS questionnaire	Patient-completed validated questionnaire which defines presence, type and severity of LUTS	Total score (0-35)	Study Visit, Part A

Frequency volume chart* ∞	A patient-completed/automated diary (at least 3 days) of the volumes and timing of urine passed.	Waking (day) time frequency, sleeping (night) time frequency, 24 hour voided volume, nocturnal voided volume, average volume voided each void	Given in Patient Information Pack - Patient completes at home
Uroflowmetry*	'A measurement of urine flow rate and voided volume as a function of time, either in the clinic or at home. Patients in the PriMUS study will perform uroflowmetry at home using the Flowtaker device.	Maximum flow rate, voided volume against normal age-adjusted range. Single value in mL/s	Given in Study Visit, Part B - Patient completes at home
Post void residual*	Simple abdominal ultrasound scan to determine the volume of urine remaining in the bladder after urination.	Residual volume against normal age-adjusted range. Single value in mL	At Study Visit , Part B

**Table 1:** Index tests to be used in model development. Non-discriminatory tests will be excluded in final model. \*Not currently available and/or in routine use in Primary Care. ∞ Also used to characterise presence of nocturnal polyuria as an addendum

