### 3.2 Study Schema

## 4 Background

The syndrome of lower urinary tract symptoms (LUTS) occurs mostly in older men and is a bothersome condition detrimental to quality of life (QoL). It can usually be managed without invasive treatment and is very rarely a threat to life or long term health. Male LUTS accounts for four presentations each month in an average sized GP practice (CPRD, 2014). This rate of presentation makes it difficult for GPs to gain sufficient expertise to be confident about diagnosis and management. Consequently, men are frequently referred to urology specialists who often recommend treatments that could have been initiated in primary care. Clinical uncertainty also leads to variation in referral patterns between individual GPs, practices and localities. To address this, the National Institute for Health and Care Excellence (NICE) issued guidance for Male LUTS in 2010 (revised 2015) mapping out initial assessment and conservative management within primary care [1]. Despite this the proportion of men referred to urology services following an incident presentation of LUTS rose from 10% in 2009 to 30% in 2013 (CPRD 2014) at an approximate extra cost to NHS England of £2 million. Implementation projects commissioned by the NHS concluded that further support with access to simple accurate tests, diagnostic protocols and decision aids was needed to facilitate patient management in primary care and ensure best value for patients and the NHS from specialist referral [2].

One of the difficulties faced in primary care is obtaining and interpreting simple clinical measurements that differentiate causes of male LUTS and hence guide effective symptom management. The underlying conditions that disturb lower urinary tract function, with their approximate prevalence are: detrusor overactivity (57%), bladder outlet obstruction (31%), and detrusor underactivity (16%). The diagnoses may appear individually or in combination. An additional contribution to male LUTS arises from ageing-related changes in fluid homeostasis which commonly result in nocturnal polyuria (30%) diagnosed from a 24-hour record of urine output. Nocturnal polyuria, although not a urodynamic abnormality, must be considered when making a diagnosis in men with nocturia as a prominent symptom. About a third of men with LUTS have a combination of two or more underlying causes [3, 4].

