## **11.2 Clinical Assessments /Data Collection**

For men who are willing and consent to participate, results of the required index and reference tests will be recorded as they are performed. This will be co-ordinated by the research nurse for the study at each hub aided by primary care records and Research Network support. GPs will complete the Patient Eligibility Checklist, which will confirm that the patient is eligible to enter the study. The results of these tests will not be detailed on the Patient Eligibility Checklist. Data collected from the index tests performed by the GP during the first GP consultation will be documented on the Patient Eligibility

Results form. The potential participants will be required to complete and sign a Consent to Contact Form, confirming that they are happy to be contacted by the research nurse and giving permission for their medical records to be reviewed, so that research nurses can follow up any results of the index tests that aren't readily available immediately following the initial GP consultation (i.e. PSA test).

The results of the tests will be compiled into a results report form, which will subsequently be sent to the GP for further symptom management. The study research nurse performing the urodynamics will not have knowledge of all the results of the index tests when performing and analysing the reference test, only those needed to inform the urodynamic procedure.

As detailed in Table 2 below, the minimum dataset will comprise: age (years), bladder exam (palpable/not palpable), digital rectal exam (mild/moderate/severe enlargement), PSA ( $\geq 1.5$  pg/mL or  $< 1.5$  pg/mL) and as an absolute value, symptom score with storage, filling and QoL components, uroflowmetry ( $Q_{\max}$  in mL/s and  $V_{\text{void}}$  in mL), residual volume (mL), frequency volume chart [Waking (day) time frequency, sleeping (night) time frequency, 24 hour voided volume, average voided volume, nocturnal voided volume]. The variables from urodynamics will include a 3-item quality control checklist; zeroed to atmospheric pressure, adequate subtraction of abdominal pressure and detrusor pressure starting at zero ( $\pm 5$  cmH2O), detrusor overactivity on filling (Yes/No), BOOI ( $> 40$  or  $\leq 40$ ), BCI ( $< 100$  or  $\geq 100$ ), and absolute values for both BOOI and BCI.

Table 2		Initial GP Consultation		Study Visit (Either 1 Visit or 2 Separate Visits)	

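### The rectal examination result has three levels, all of them degrees of enlargement, so the protocol as written gives no code for a prostate that is not enlarged

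*Protocol*

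**What the plan says.** Section 10.2, Table 1 lists each index test with the result to be recorded. For the digital rectal examination the size result is "Prostate mild/moderate/severe enlargement". A second line in the same cell reads "Further assessment for prostate cancer required/not required". The stated purpose of the examination is "To determine prostate enlargement and likelihood of locally advanced prostate cancer". The row above it, for the abdominal examination, is recorded as "Bladder palpable/not palpable".

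Section 11.2 sets out the minimum dataset and repeats the same scale: "digital rectal exam (mild/moderate/severe enlargement". The same sentence gives a PSA cut at 1.5 and continues "pg/mL) and as an absolute value, symptom score with storage, filling and QoL components".

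Section 8.1 admits "Men aged 16 years and over" who present with at least one bothersome urinary symptom. An enlarged prostate is not an entry criterion.

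The note under Table 1 says that these tests feed model development and that tests which do not discriminate are dropped. Sections 16.2 and 17.1 say that missing values will be filled by multiple imputation (chained equations, 10 datasets for each cohort) from the distribution of the observed data. Section 10.1 has primary care staff entering index test results into the aid's online form.

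**The concern.** A scale that begins at mild enlargement presupposes that every examined prostate is enlarged. The protocol does not suppose this: the examination is there to find out, and men are admitted on symptoms. A GP who follows the written scale and finds no enlargement has two choices, to tick mild or to leave the item blank.

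Either choice affects a candidate predictor in all three models. Ticking mild mixes two groups in the lowest level. Leaving it blank makes the missingness depend on the value that was not recorded, and imputation cannot then restore a level that never appears in the data. Practices may also settle the matter differently, and section 7 plans for 100 of them; that would add variation unrelated to the prostate. If the predictor survives selection, a GP using the finished aid would have no correct entry for such a patient.

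**Working it through.** **The places that define the result.** Table 1 and the section 11.2 dataset both give mild, moderate and severe enlargement. No other section of the protocol gives a further level. The repetition makes a slip confined to one table unlikely.

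**Whether another field could carry the negative finding.** The second line of the Table 1 cell concerns cancer work-up only. A man can need no further cancer assessment with or without an enlarged prostate, so that field does not record size.

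**Whether the protocol expects a negative finding.** Three features of the text say that it can occur:
- The purpose in Table 1 is to establish enlargement, which allows the answer no.
- The neighbouring abdominal examination has a negative level.
- Section 8.1 does not require enlargement for entry.

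**What imputation would do with blanks.** If the observed levels are {mild, moderate, severe}, a method that draws plausible values from the observed distribution returns one of those three. The probability of imputing not enlarged is 0, whatever the man's age, PSA or other covariates.

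**How many men.** The protocol gives no share of men without enlargement. Call it p and assume 10% to 50%, purely to show the scale:

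| p (assumed) | Development, 350 × p | Validation, 325 × p | Both, 675 × p |
|---|---|---|---|
| 0.10 | 35 | 32.5 | 67.5 |
| 0.20 | 70 | 65 | 135 |
| 0.50 | 175 | 162.5 | 337.5 |

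**What the extra level costs in model terms.** Section 16.1's own figure reproduces: 350 × 0.16 = 56 events of detrusor underactivity, and 56 / 5 = 11.2, so up to 11 variables at 5 events per variable. A three-level factor uses 3 − 1 = 2 indicator terms and a four-level factor uses 4 − 1 = 3. The change costs at most one of the 11 terms, or none if the grades enter as a single ordinal score. The sample size is unaffected.

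**The other two items in the section 11.2 sentence.** Table 1 gives PSA in ng/mL, whereas section 11.2 gives the same 1.5 cut in pg/mL. Since 1 ng = 1000 pg, the labels differ by a factor of 1000. Table 1 gives the ICIQ total as 0–44, made up of voiding 0–20 and storage 0–24 (20 + 24 = 44), so voiding and storage are the two symptom components. Section 11.2 names storage and filling and omits voiding.

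**The case against.** The strongest reply is that Table 1 is a summary and not the recording instrument. GPs complete the Patient Eligibility Results Form, which is not in the document, and no section says that the three grades are the only permitted answers. They can be read as grades to use when enlargement is present. This stands: the gap is shown for the protocol text, not for the form. It does not remove the point, because the protocol's dataset definition is what the form and the aid should follow.

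Safeguards against blanks also exist. GPs must sign the results form, staff are trained and given a manual (section 11.1), missing items are queried (section 18.4), and patterns of missingness are examined (section 16.2). These make the blank-then-imputed route less likely. They do not supply a correct code, so a query could simply turn a blank into mild.

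On the size of the harm, the models also contain age, PSA, flow rate, residual volume and symptom scores. Predictor distributions are inspected before selection, and the LASSO may drop the examination altogether (section 17.1.1). A lowest level that mixes none and mild still separates those men from the moderate and severe groups. All of this limits the harm to some loss of information, and possible bias, in one predictor.

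A reader might infer from the Background's prevalences (detrusor overactivity 57%, obstruction 31%) that many men will have a normal-sized prostate. That does not follow: these are overlapping urodynamic diagnoses and say nothing about prostate size. The age limit of 16 is only a lower bound, and the Background says that the condition occurs mostly in older men.

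A reader might also infer that the PSA data will be wrong by a factor of 1000 or that the voiding score will be lost. Neither is supported. PSA is also kept as an absolute value, Table 1 specifies it as continuous in ng/mL for the aid, and section 17.1.1 rules out categorising continuous variables. The voiding score is specified in Table 1. Both are clerical errors.

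**Conclusion.** The point holds for the protocol as written. Both definitions of the rectal examination result omit a not-enlarged level that the purpose of the test and the entry criteria require. If data are captured that way, men without enlargement are merged into mild or left missing, and imputation could place them only in an enlarged category. The consequence is lost information and possible bias in one candidate predictor across the three models, plus a gap in the aid's input form if the predictor is retained.

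The number of men affected cannot be derived from the document. The 35 to 175 development men rest wholly on an assumed 10% to 50%, and no effect on sensitivity or specificity can be calculated. The conclusion also depends on the results form following the protocol. If it already offers a normal box, only wording needs to change.

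A reader might conclude that the information is irretrievably lost. The documents do not support that: the examination is done and recorded by the GP, so the practice record may supply the finding for men already seen.

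**What to change.** In Table 1 and in the section 11.2 dataset, change the size result to not enlarged / mild / moderate / severe. Make the Patient Eligibility Results Form and the aid's input form agree. For men already examined, check the GP record and recode where it shows no enlargement. Count at most one extra term against the 11 allowed for the detrusor underactivity model, or none if the grades are fitted as an ordinal score.

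As minor corrections in the same section 11.2 sentence, change the PSA unit to ng/mL and name the symptom components as voiding and storage, so that both agree with Table 1.

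The cost is one extra response option, a wording amendment and a record check. No further examination, participant or visit is needed. The change is best made early, since each man recorded on the present scale may need a later check.
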